5.5.2.3 Safety measures

The following safety outcome measures will be collected:

- duration of hospital admission associated with the index stroke (comprising associated acute and community inpatient stays where appropriate)
- death, and cause of death where known,
- readmissions to hospital and primary cause of readmission,

5.5.2.4 Measures of Treatment As Usual (TAU)

TAU will be captured in two ways.

At **site level**, the **profile of TAU** (e.g., average neglect therapy time, frequency, type of therapy and location) will be recorded by the senior stroke occupational therapist at each centre at start of recruitment when the site opens, during the recruitment period, and at end of recruitment.

At **individual patient level**, the therapy delivery staff will record the frequency, duration, location, and overall content (e.g., visual and scanning therapies) of each TAU session the participant receives during the 10-day period of intervention using a study-specific therapy booklet placed in the patient's bedside developed with clinical teams and adapted from our c-SIGHT and SPATIAL feasibility studies.

5.6 Participant Timeline

Figure 3. Schedule of SIGHT enrolment, baseline assessments, allocation to treatment arm, intervention treatment period, and post-intervention assessments.

	STUDY PERIOD					
	Enrolment	Baseline	Allocation	Intervention	Post- Treatment	
TIMEPOINT	t-1	T ₀			T ₁	T ₂
Initial screen	Х					
Informed consent	Х					
MRI Screening	X					
Star Cancellation BIT	X	X**			x	x
BIT Line Bisection	X	X**				
OCS Cancellation	X	X**			x	x
Endpoint Weightings Line Bisection		Х			x	x
Catherine Bergego Scale KF-NAP		х			x	x
Safety outcome measures		х		x	x	x
Stroke Impact Scale						x
Demographics		х				
Clinical Data		х				
Full OCS		x				
NIHSS		Х				
VISA visual fields		х				1

CENT***	Х			
Gesture recognition BCoS	х			
T1 Structural Weighted Scan	X*			
T2 FLAIR	X*			
Diffusion Weighted Imaging Scan	X*			
Resting-state Functional MRI	X*			
Allocation		х		
[Arm A – Treatment as Usual TAU]			х	
[Arm B – SIGHT Intervention + TAU]			x	

*Mechanistic neuroimaging measures only for participants who are suitable and consent at sites that have an available 3T MRI scanner.

** These measures may be recorded at screening/eligibility confirmation and should be repeated at Baseline (T0) unless screening/eligibility confirmation and T0 are done on the same day

*** Optional measure for sites that have the appropriate equipment

5.6.1 Patient Assessments

5.6.1.1 Screening and Consent

All the screening and consent procedures should be completed within the 1-week to 60 days post-stroke window. Once initial screening has been completed, informed consent to enter and be randomised into the trial must be obtained from the potentially eligible participants or their consultee after explanation of the aims, methods, benefits and potential hazards of the trial and before any trial specific procedures. In addition, if the participant agrees, a letter will be sent to the participant's GP detailing their involvement in the trial. The only procedures that may be performed in advance of consent being obtained are those that would be performed on all patients in the same situation as a usual standard of care.

5.6.1.2 Baseline (T0)

Once the participant or consultee has given informed consent/assent and eligibility has been confirmed (signs of neglect on at least one of the following: Star Cancellation ≤51; or BIT Line bisection score ≤7; or Oxford Cognitive Screen cancellation accuracy <42 as well as either Oxford Cognitive Screen Cancellation Object score >1 or < -1, or Oxford Cognitive Screen Cancellation Space score >3 or < -2), local site staff will collect the baseline measures consisting of: demographic and clinical data; Star Cancellation sub-test of the BIT; Line Bisection sub-test of the BIT; cancellation task of the OCS; endpoint weightings line bisection; the Catherine Bergego Scale KF-NAP (CBS KF-NAP); NIHSS; Perception-Grasping dissociation task; visual field assessment sub-test of the VISA tool; the Oxford Cognitive Screen (OCS), Gesture Recognition sub-test of Birmingham Cognitive Screen (BCoS) and the **optional** Computerised Extrapersonal neglect test (CENT). To account for patient fatigue, these measures can be grouped together and done at different times or on different days to allow for a rest period.

5.6.1.3 Randomisation – Day 0

The completion and submission of the baseline measures will enable the database randomisation notifying the trial team and local SIGHT intervention delivery staff of the patient's trial arm. Randomisation stratification will use trial site, age of patient, neglect severity (according to the Star Cancellation) and whether a lesion is present or not on the Intraparietal Sulcus (IPS).

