4.3 Trial Design

This is a multi-centre randomised, controlled, assessor-blind, 2-group (TAU alone and SIGHT+TAU) efficacy trial with an embedded mechanistic study to test determinants of therapy response.

Participants will complete efficacy and mechanistic measures at baseline (T0). Where NHS trusts have the capacity and participants are able and consent to an MRI, they will complete mechanistic neuroimaging measures at baseline (T0) as well. Participants will be randomised, considered Day 0, to one of the two groups after baseline measures are completed. The intervention group will receive seven 30-minute SIGHT sessions over a 10-day period. Both groups will receive usual care (TAU). The efficacy outcomes taken at baseline will be repeated at Day 11 (T1) and 12 weeks (T2) post-randomisation.

Randomisation will be implemented by a secure web-based service provided by the NCTU after T0 measures are collected. Randomisation sequence will be stratified by clinical centre and will balance the following evidence-based factors across groups: age (<65 or \geq 65), neglect severity (0-25 very severe or 26-51 less severe on Star Cancellation Test [17]) and preservation of the IPS (yes or no) assessed with routine clinical imaging. Age and neglect severity are included as these have been shown to significantly impact stroke recovery [59;38-39]. IPS lesion is included to balance our groups for the mechanistic analysis. Time after stroke was not included as our inclusion criteria of participants being 'less than 60-days post-stroke' will ensure that all participants will complete intervention within the first 90-days post-stroke (i.e., early subacute phase [32]), which is the recommended period for all stroke recovery trials as it is a critical time for neural plasticity [31-33]. In a similar vein, participants will also be 'at least 1-week post-stroke' thus avoiding the inclusion of the 30% of patients that show rapid neglect recovery in the first week post-stroke [86].

The research staff delivering therapy at each site will be notified of group allocation via the NCTU secure web-based service. Group allocation will be withheld from other members of the Trial Team, the recruiting staff in each stroke service and the blinded assessors. To reduce the risk of contamination, SIGHT will be delivered in a separate treatment room and onsite monitoring of intervention delivery will review trial progress and discuss the importance of this risk.

5 Methods

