- The OCS is an established quick (15min) cognitive screen consisting of 10 tasks encompassing five cognitive domains: attention and executive function, language, memory, number processing, and praxis [45]. The OCS was devised to be inclusive and un-confounded by aphasia and neglect. The OCS offers advantages over other screening tools in terms of ease of completion and feasibility for stroke survivors with physical, language or visuospatial impairments [69]. Moreover, the OCS is more sensitive than the Mini Mental State Examination at detecting cognitive deficits poststroke [70] and assesses stroke-specific cognitive deficits not assessed by the Montreal Cognitive Assessment or the Addenbrookes Cognitive Examination [71].
- The gesture recognition sub-test of the BCoS (5min) will be used to provide quick and valid way to detect apraxia using procedures designed to be inclusive for patients with aphasia and/or spatial neglect [76]. Participants will view familiar gestures (object and non-object related) and asked to choose their meaning. As we are recruiting both right, left and bilateral hemisphere strokes this will help examine whether those with apraxia in our sample are able to benefit from SIGHT.
- **CENT** (5min) is a sensitive computerised 'aphasia friendly' measure of neglect of far space (or extrapersonal neglect) that has been validated in stroke and shown to predict stroke recovery and ADL deficits [77,87]. Participants are asked to use a mouse to click on targets on a screen. The scores are automatically generated.
- The clinical brain imaging scans (CT and/or MRI) and their reports will be extracted and used to map the stroke lesion location. Lesions will be manually delineated by UEA team on the structural scan using open-source cross-platform medical image viewers such as MRICROn 72]. Then, the checked lesion maps will be normalized to stereotaxic space using the age-specific template within the Statistical Parametric Mapping Software (SPM) clinical toolbox developed for stroke lesion-symptom mapping studies [73]. Routine clinical brain scans have been demonstrated to be of sufficient quality for lesion mapping research [74-75] and will ensure that lesion mapping can be performed for the full sample (N=206), instead of only those who complete the MRI (N=80), giving us sufficient power (minimum recommended N=100 [75]) for determining the lesion locations significantly associated with lower therapy response.

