Anonymised neuroimaging data will be sent to UEA research team via the Image Exchange Portal and processed using specialist software such as SPM and FSL. We will use well-established pre-processing routines for motion-correction, coregistration, smoothing and temporal filtering, and standardised pipelines that facilitate comparisons across studies (e.g., fMRIprep). Regions of interest (ROIs) will be manually identified in each participant in left and right IPS (seed regions) by visual inspection of the T1 using established anatomical landmarks and then centring a sphere closest to the peak coordinates associated with neglect improvement [28]. ROIs overlapping with lesion will be excluded from analysis.

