5.10.4 Statistical Methods

5.10.4.1 Outcomes

Analysis will be conducted according to random group allocation (intention-to-treat principle). Baseline characteristics of the participants will be summarised using descriptive statistics by groups, n (%) for binary and categorical variables and mean (SD)/median (QIR) for continuous variables. Flow of the participants through the trial will be reported using the CONSORT flow diagram. A descriptive summary of the treatment received as well as adherence and fidelity measures will be given. A full statistical analysis plan will be pre-registered prior to completion of data collection, thus adhering to open and replicable research practices.

The clinical efficacy analysis will compare continuous outcome variables between treatment groups, using a general linear model at each time-point separately adjusting for stratification factors. To account for potential TAU variability across sites, clinical centre will be used as a co-variate. The effect of treatment will be summarised using the adjusted mean difference and 95% confidence interval. Dependent variables will include: Star Cancellation score (primary), CBS KF-NAP score, line bisection error and OCS Hearts overall, ego- and all centric scores and SIS scores in each domain.

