5.12.3.4.4 Independent Data Monitoring Committee

The Independent Data Monitoring Committee (IDMC) is the only oversight body that has access to unblinded accumulating comparative data. The IDMC is responsible for safeguarding the interests of trial participants, monitoring the accumulating data and making recommendations to the TSC on whether the trial should continue as planned. The membership, frequency of meetings, activity (including review of trial conduct and data) and authority will be covered in the IDMC terms of reference. The IDMC will consider data in accordance with the statistical analysis plan and will advise the TSC through its Chair.

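### The protocol disagrees with itself on who learns the allocation, and the hand-drawn lesion maps and IPS seed regions carry no masking requirement

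*Protocol*

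**What the plan says.** Section 4.3 (Trial Design) names one group that is told the arm: "The research staff delivering therapy at each site will be notified of group allocation via the NCTU secure web-based service". It then lists who is not told: "Group allocation will be withheld from other members of the Trial Team, the recruiting staff in each stroke service and the blinded assessors".

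Section 5.6.1.3 (Randomisation – Day 0) says that submitting the baseline measures triggers "database randomisation notifying the trial team and local SIGHT intervention delivery staff" of the arm assigned to that patient.

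Three further sections bear on the same question:

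- Section 5.4.3 (Accountability) has database checks that tell NCTU operations and site staff which participants are in the intervention arm.
- Section 5.9.1.3 (Allocation Implementation) sends an email to assigned research team members, whose roles are not given, and stores the randomisation code in the study database.
- Section 5.9.2 (Blinding) withholds allocation from the blinded assessors and mentions nobody else.

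On imaging, section 5.5.2.2 states: "Lesions will be manually delineated by UEA team on the structural scan". It also says that regions of interest "will be manually identified in each participant in left and right IPS (seed regions) by visual inspection of the T1". Neither statement mentions masking to arm or to outcome.

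**The concern.** The statements in 4.3 and 5.6.1.3 cannot both be followed. Section 5.6.1.3 lists the trial team alongside the local delivery staff, so the term there cannot simply mean those staff.

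The mismatch matters most for the mechanistic study. Lesion extent and seed position are judgements made by eye. They supply predictors for the second hypothesis, that patients with impaired IPS structure or function benefit less from SIGHT. If the person drawing knows the arm, borderline calls could differ by arm, and the arm-specific and interaction tests are the ones that would absorb the difference. The protocol neither says that this can happen nor rules it out.

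**Working it through.** No arithmetic is needed beyond a count, so the check sets the sections side by side.

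**Who is told the arm**

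- 4.3: staff delivering therapy.
- 5.6.1.3: the trial team and local delivery staff.
- 5.4.3: NCTU operations and relevant site staff, for intervention-arm participants.
- 5.9.1.3: research team members assigned to the patient, roles unspecified.

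**Who is masked**

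- 4.3: other Trial Team members, recruiting staff and blinded assessors.
- 5.9.2: blinded assessors only.

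Sections 5.4.3, 5.6.1.3 and 5.9.2 are compatible with a central team that knows the arm; 4.3 is not. Section 5.1.2.4 points the same way, because the central team monitors fidelity checklists completed at SIGHT sessions, and these exist only for the SIGHT arm. Section 4.3 may therefore be the outlier, but no sentence says which statement governs.

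**Whether the people drawing lesions and seeds could be among those told**

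1. Section 5.10.2 restricts the database and the brain images to members of the SIGHT trial team. Section 5.6.1.3 uses the same general term for those notified.
2. Section 5.5.2.2 assigns lesion delineation to the UEA team and sends the neuroimaging data to the UEA research team.
3. The term trial team is not defined in the text at hand. The overlap is therefore possible but not shown.
4. Pseudonymising scans (5.10.2) removes identity. It does not mask arm for anyone who can link the participant number to a database holding the allocation.
5. Section 5.10.1 requires blinded scoring of the paper-based assessments. It does not extend to image delineation.

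**Where the hand judgements enter the analysis**

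- Seeds that overlap a lesion are excluded (5.5.2.2), so the drawn boundary decides which seeds are analysed.
- Lesion volume, computed from the same map, is regressed out when change scores are correlated with the mechanistic measures (5.10.4.1).
- The maps are the input to the lesion-symptom mapping for hypothesis 2 (5.10.4.1).
- IPS effects are tested in each arm separately and by interaction (5.10.4.1).

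**Count exposed**

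- Lesion maps: up to 206, the full sample.
- IPS seeds: 80 MRI participants × 2 (left and right) = 160 placements, before exclusions.

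**The case against.** The strongest reply is that no sentence sends allocation to the imaging raters. The protocol uses the term trial team loosely, sometimes for NCTU staff and in 5.10.1 even for people working at sites, whereas lesions are drawn by the UEA team. A reader might infer from 5.6.1.3 that the raters are told each patient's arm, but the documents do not establish that. Nor does any section give raters the T1 change scores.

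The imaging procedure also has safeguards:

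- Research scans are acquired before the other baseline measures, and so before randomisation.
- The IPS yes/no stratification factor is recorded before randomisation.
- Seeds follow anatomical landmarks and published peak coordinates.
- Exclusion for lesion overlap is a stated rule.
- Lesion maps are checked before they are normalised.

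These points narrow the room for judgement but leave a gap. Scanning before randomisation does not mean drawing before randomisation, and no deadline for delineation is given. A landmark-guided placement made by eye is still a judgement, and the overlap rule depends on where the lesion edge was drawn.

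A reader might also take 5.10.4.1, where "A full statistical analysis plan will be pre-registered prior to completion of data collection", to mean that analysis choices could be made late with knowledge of arm and so weaken the efficacy result. That is not supported. Registering the plan before data collection ends is not an error. The protocol already fixes the primary outcome, the model and the stratification and centre adjustment. Section 5.12.3.4.4 says that the IDMC "is the only oversight body that has access to unblinded accumulating comparative data". T1 and T2 assessors are blinded, and the paper tests are scored blind.

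Section 5.1.2.4 allows staff who randomise to deliver SIGHT as well. That is not a breach of 4.3 in itself, because such a person is delivering therapy.

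**Conclusion.** The contradiction between 4.3 and 5.6.1.3 is exact, and 5.4.3, 5.9.1.3 and 5.9.2 do not resolve it. As written, central team members need not be masked to allocation. Those who hand-draw lesions and place IPS seeds may be among them, since nothing in 5.5.2.2 requires masking.

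The exposure is confined to the mechanistic analyses: seed exclusion, lesion volume, lesion-symptom mapping, and the arm-specific and interaction tests. The size and direction of any bias cannot be derived from the protocol. Blinded measurement of the primary outcome at T1 and T2 is not affected, and the finding says nothing against the confirmatory standing of the efficacy comparison.

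The conclusion rests on two readings: that the trial team in 5.6.1.3 includes people beyond the local delivery staff, which the sentence itself implies, and that it could include imaging raters, which the text leaves open. The change should be made, because it closes a route to bias at little cost.

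**What to change.** **Reconcile 4.3, 5.4.3, 5.6.1.3, 5.9.1.3 and 5.9.2 together.** Name the roles that receive allocation, namely the staff delivering SIGHT and the specific NCTU or central roles that need it for intervention and fidelity support, and use the same list in each section. Editing 5.6.1.3 alone to match 4.3 would leave NCTU operations notified under 5.4.3, the email recipients undefined in 5.9.1.3 and the narrower masking statement in 5.9.2.

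**Add to 5.5.2.2** that lesion delineation and region-of-interest placement or exclusion are done masked to allocation and to T1 and T2 scores, and are locked before allocation is merged with the imaging data.

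The cost is wording in five sections, one added statement, and notification and permission settings in the database. No extra staff, readers or participants are needed. The one practical burden is that fidelity support and imaging work must be kept apart within the central team.

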5.6.1.4 Intervention and treatment as usual – within 10 Days Post-Randomisation

If a patient is allocated to the intervention arm, the SIGHT trained staff will deliver the SIGHT intervention over a 10-day period following randomisation. Treatment as usual will be recorded during this 10-day period for all patients on both arms of the trial.

5.6.1.5 Follow Up (T1) Efficacy Measures – Day 11 (+5 days)

All participants will have a visit from a blinded assessor on Day 11 (+5 days) postrandomisation. The blinded assessor will collect the efficacy measures: Star Cancellation test; endpoint weighting line bisection, OCS and the Catherine Bergego Scale KF-NAP.

5.6.1.6 Follow Up (T2) Efficacy Measures – 12 Weeks (±10 days)

All participants will have a visit from a blinded assessor at 12 weeks (±10 days) postrandomisation. The blinded assessor will collect the efficacy measures: Star Cancellation test; endpoint weighting line bisection, OCS; the Catherine Bergego Scale KF-NAP and the Stroke Impact Scale (SIS).

5.6.2 Early Stopping of Follow-up

If a participant chooses to discontinue their trial treatment, they should continue to be followed up as closely as possible to the follow-up schedule defined in the protocol, providing they are willing. They should be encouraged and facilitated not to leave the whole trial, even though they no longer take the trial treatment. If, however, the participant exercises the view that they no longer wish to be followed up, this view must be respected and the participant withdrawn entirely from the trial. NCTU should be informed of the withdrawal using the appropriate SIGHT trial documentation as soon as possible. Deaths should also be reported as a withdrawal. Data already collected will be kept and included in analyses according to the intention-to-treat principle for all participants who stop follow up early.

Randomised participants who stop trial follow-up early will not be replaced. Recruitment will be monitored by DMEC and if recruitment is below expected due to drop-outs trial team may seek approvals to increase sample size.

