5.4.6 Protocol Treatment Discontinuation

In consenting to the trial, participants are consenting to trial treatments, trial follow-up and data collection. However, an individual participant may stop treatment early or be stopped early for any of the following reasons:

- A new diagnosis of a pathology or adverse event that impacts the participant's ability to take part in the trial or confounds response to SIGHT, e.g., cancer, upper limb fracture.
- Any change in the participant's condition that in the clinician's opinion justifies the discontinuation of treatment.
- Withdrawal of consent for treatment by the participant.
- Participant moves out of catchment area of clinical centre (acute or community).
- Death

As participation in the trial is entirely voluntary, the participant may choose to discontinue trial treatment at any time without penalty or loss of benefits to which they would otherwise be entitled. Although not obliged to give a reason for discontinuing their trial treatment, a reasonable effort should be made to establish this reason, whilst remaining fully respectful of the participant's rights.

Data collected up to the date of withdrawal will be retained and included in data analysis.

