5.11.2 Safety reporting

Adverse events (serious and non-serious) will not be collected in this study.

This is a low-risk intervention. No specific risks, untoward incidents or adverse events related to the intervention were reported during development, testing and pilot work. Nine adverse events unrelated to the intervention were reported in the pilot including three deaths; five hospital admissions (due to new stroke event, infection, fall, progressive disease); and one participant was referred to end of life care'. The SIGHT neurorehabilitation intervention therapy is delivered to participants by trained therapists. If participants encounter issues with the materials provided, these will be reported by the therapist to the research team where they will be collated into an Incident Log. The participant has the right to decline any intervention at any time.

At the time of recruitment, all participants will be inpatients in acute or community hospitals. The occurrence of common complications arising from stroke, including: 1) clinical complications such as pneumonia, urinary tract infection, pressure damage and deep vein thrombosis; and 2) neurological complications such as malignant ischemic stroke and symptomatic haemorrhagic transformation, would not be influenced by intervention, although these complications may impact the delivery of the intervention. Reasons for an intervention session not being delivered as anticipated or stopped early will be recorded in the database. However, as stroke and complications arising from the stroke, is associated with increased risk of death, increased duration of hospital stay (acute and community settings as appropriate), and readmissions, the following safety data will be collected during the study:

- death (and cause)
- length of hospital stay (comprising of total of acute and community inpatient settings as appropriate)
- readmissions to hospital (including reason)

Reasons for withdrawal will also be used to ascertain any potential safety issues, including referral to end of life care.

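### Section 5.6.2 has no step between full follow-up and complete withdrawal, so later deaths, readmissions and length of stay can be lost for participants who leave

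*Protocol*

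**What the plan says.** Section 5.6.2 (Early Stopping of Follow-up) distinguishes two situations. A participant who stops only the trial treatment is encouraged to stay in follow-up. If participants "no longer wish to be followed up, this view must be respected and the participant withdrawn entirely from the trial". For those who stop early, "Data already collected will be kept and included in analyses according to the intention-to-treat principle". Section 5.4.6 (Protocol Treatment Discontinuation) sets the same limit: "Data collected up to the date of withdrawal will be retained and included in data analysis". No intermediate state is described.

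Section 5.6.3 (Participant Transfers) adds a withdrawal that the participant does not choose: a patient who moves from the consenting acute hospital to a site outside the trial is withdrawn.

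Section 5.5.2.3 lists three safety outcomes:
- "duration of hospital admission associated with the index stroke"
- "death, and cause of death where known"
- "readmissions to hospital and primary cause of readmission"

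Section 5.11.2 repeats them and says that adverse events are not collected. It adds: "Reasons for withdrawal will also be used to ascertain any potential safety issues, including referral to end of life care". Section 5.6.2 also says: "Deaths should also be reported as a withdrawal".

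**The concern.** Refusing more visits and tests is different from refusing all further data collection. Section 5.6.2 does not separate them. A site that follows the text has no option under which visits end but the safety outcomes continue to be recorded.

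This matters because section 5.11.2 rests the safety assessment on these three outcomes, and section 5.11.1 plans no additional safety endpoints. Section 5.11.2 treats the reason for withdrawal as a possible safety signal and expects some withdrawals to involve referral to end of life care. Under sections 5.4.6 and 5.6.2, collection ends at that point, so what happened next is not recorded. If those who leave are sicker than those who stay, each arm's counts of deaths and readmissions will be too low, and the between-arm comparison will rest on a selected group. An analysis plan cannot recover data that were never collected.

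**Working it through.** **1. What is kept and what is lost**

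| Situation | Kept under the protocol | Lost |
|---|---|---|
| Stops SIGHT, stays in follow-up (5.6.2) | Everything to 12 weeks | Nothing by rule |
| No longer wants follow-up (5.6.2) | Data up to withdrawal, and the reason where given | Later death and readmission; discharge date if still an inpatient |
| Moves to a non-participating site (5.6.3) | Data up to withdrawal | The same |
| Dies while in the trial (5.6.2) | The death, reported as a withdrawal | Nothing by rule |

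**2. Do the safety outcomes depend on an assessor visit?** Sections 5.6.1.5 and 5.6.1.6 list what the blinded assessor collects at T1 and T2: Star Cancellation, endpoint weightings line bisection, OCS and CBS KF-NAP, plus SIS at T2. The three safety outcomes are not listed there. Figure 3 schedules safety measures at baseline, during the intervention, at T1 and at T2, without naming a source. Collection from hospital records is therefore plausible but not stated.

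**3. The plan's own figure.** Section 5.7 gives an effect size of 0.51, 90% power, the 5% level (taken as two-sided), a two-sample t-test and 20% dropout.
- Required per group: 81.8, so 82.
- Inflated for dropout: 82 / (1 − 0.20) = 102.5, so 103.
- Total: 2 × 103 = 206, which reproduces the protocol. The point below does not change the sample size.

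**4. Upper bound on the number affected.** The documents do not split dropout by type.
- At 20%: 0.20 × 206 = 41.2, about 41.
- If 10% fully withdraw (assumed): 20.6, about 21.
- If 5% fully withdraw (assumed): 10.3, about 10.

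**5. Share of events missed, as a range under assumptions.** Let w be the proportion withdrawn and r the event risk in withdrawn participants relative to the others. If all events in withdrawn participants fall after withdrawal, the share missed is

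w·r / [(1 − w) + w·r].

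For w = 0.20 and r = 2: 0.40 / (0.80 + 0.40) = 33%.

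| w | r = 1 | r = 2 | r = 3 |
|---|---|---|---|
| 0.05 | 5% | 10% | 14% |
| 0.10 | 10% | 18% | 25% |
| 0.20 | 20% | 33% | 43% |

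Both w and r are assumed. Events before withdrawal are kept, so the true share for a given w and r would be lower.

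**The case against.** The strongest reply has five parts.

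- **The trigger is wider than refusing visits.** Section 5.6.2 concerns someone who does not want follow-up at all. A reader might infer that a site must stop all collection for a person who only dislikes more testing at home. No sentence says so. Section 6.5 lets participants refuse the whole trial or any part of it, and section 6.1 expects randomised participants to remain for follow-up, subject to their own choice. This stands as a limit on the claim. But a right to partial refusal supports having levels; it does not supply them.
- **The levels may exist elsewhere.** Section 5.6.2 refers to trial documentation for reporting withdrawal, which is not shown. That form may be more detailed, but it would not override the rule the protocol states.
- **Some safety information survives.** Events before withdrawal are kept, deaths in the trial are reported, and withdrawal reasons are reviewed. This is true, but none of it captures later events.
- **Transfers may be few.** Section 5.3.1.3 excludes patients expected to go home, or to a facility outside the regional hub, within 7 days. That reduces the number affected by section 5.6.3 but does not cover later or unplanned moves.
- **Unequal loss by arm is not shown.** A reader might infer it from the pilot, where 37.5% dropped out through dislike of the sham. Section 4.1.1 explains that the sham was replaced by usual care for that reason, so the figure does not carry over to this comparison.

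**Conclusion.** The point holds as a gap in the withdrawal rule. The protocol has no state in which visits stop but passive collection of death, readmission and length of stay continues. Section 5.6.3 applies withdrawal to some patients who have refused nothing. Later events in these participants are lost, and the safety comparison may be incomplete.

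The size is uncertain. The 41 of 206 is an upper bound, because planned dropout also includes deaths and other losses that are not full withdrawals. The shares in the table are scenarios, not estimates.

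Three stronger readings are not supported:
- That those who leave are the patients most likely to have an event. The expected end-of-life referrals make higher risk plausible, but no figure shows it.
- That these outcomes certainly need no contact with the patient. No data source is named.
- That they are the only between-arm safety comparison planned. Section 5.10.4.1 says adverse events, including falls, will be recorded and compared between groups. Section 5.11.2 says they will not be collected. The two sections must be reconciled.

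This is an inexpensive improvement to the safety data. It is not a flaw in the primary analysis.

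**What to change.** Replace the rule in section 5.6.2 with three levels of stopping:

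- **(a)** Stop SIGHT only; all follow-up continues.
- **(b)** Stop visits and tests, but allow death, readmission and discharge dates to be taken from records to the end of the 12-week window.
- **(c)** Stop all data collection, only on the explicit request of the participant or consultee.

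Put the levels on the withdrawal form, and describe level (b) in the information sheets and the consent and declaration forms. Name the data source for the three safety outcomes. Treat transfers under section 5.6.3 as level (b) where the participant or consultee agrees. Bring the data-retention sentence in section 5.4.6 into line. Analyse the three safety outcomes on all randomised participants, using data up to withdrawal for those at level (c). Reconcile sections 5.10.4.1 and 5.11.2 on adverse events in the same amendment.

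The cost is one amendment with revised forms and a brief record check at site for patients who stop visits. The sample size, visit schedule and treatment are unchanged. It is best done early, because data not collected for want of permission may not be recoverable later.
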